**I. Purpose, Background and Rationale**

**A. Aim and Hypotheses**

**SPECIFIC AIMS**

We have shown that improved cardiorespiratory fitness following an aerobic exercise program elicits cognitive benefit in elderly subjects and memory improvement in Alzheimer's disease (AD). [1-3] The physiological mechanism may be related to exercise-mediated change in circulating factors that permeate the brain. The response to each individual bout of exercise (i.e. the acute exercise response) may differ between subjects and be key to driving brain benefit. In young populations, the acute response to exercise can last hours [4] and affect brain glucose metabolism. [5, 6] However, we know little about this acute exercise response in AD. Most exercise intervention trials designed to prevent and slow AD, including our own (AG033673; AG034614; AG043962; AG049749; AG053952), assess biomarkers at two fasting time points: pre- and post-intervention. The acute exercise response in the brain and periphery likely varies between subjects and diagnoses and provide key information regarding mechanisms of benefit. Our primary goals are to characterize the acute exercise response to exercise in the brain (glucose metabolism) and periphery (biomarker response) in aging and AD. We will identify relationships between exercise-related factors (i.e. heart rate, biomarkers) and change in brain metabolism and cognition. Understanding these mechanistic relationships will provide specific targets that can be used in future trials to develop individualized exercise prescriptions and maximize benefit.

Accumulating evidence suggests that the exercise-related metabolite lactate is an understudied effector of brain health. Lactate is an essential fuel for neuronal function. [7, 8] It is supplied to neurons through glucose metabolism in nearby glia [9, 10] and from peripheral blood, since the brain is permeable to lactate. [11] A drop in cerebral glucose metabolism is a marker of AD [12]. Thus, supplying neurons directly with lactate for oxidation may supplement energy requirements in AD, as has been suggested with ketones. [13] Importantly, circulating lactate levels rise during exercise [14]. Repeated increases in systemic lactate (acute exercise response) may transiently spare glucose by providing an alternative fuel. With routine exercise, acute responses may elicit adaptations that facilitate the use of lactate beyond that which occurs during acute exercise and contribute to brain benefits observed during chronic exercise interventions. In younger populations, higher exercise intensity evokes a greater lactate response compared to lower intensities [5] and elicits cognitive benefit. [15] Characterizing the acute effects of exercise intensity will greatly inform the design of future trials. We will also characterize diagnostic differences in lactate use. Finally, because acute exercise affects a variety of signaling pathways beyond lactate, we will also characterize the acute exercise response of a selected group of exercise-related biomarkers. We will achieve these goals through the following aims:

**Aim 1:** Compare the effects of acute, moderate intensity and acute, higher intensity exercise on cerebral glucose metabolism in nondemented (ND) elderly and AD subjects. ND (n=30) and AD (n=30) subjects will undergo a single bout of moderate intensity (45-55% HRR) or higher intensity (65-75% HRR) exercise to assess the effect of exercise intensity on acute change in brain glucose metabolism (rest to exercise). We hypothesize that both moderate and high intensity exercise will elicit a drop in global brain glucose

metabolism compared to quiet rest, but that the effect will be greater with higher intensity vs. moderate intensity exercise, and greater in ND subjects than in AD subjects.

**Aim 2:** Characterize the effect of both exercise intensities on acute biomarker response and cognition (memory and executive function) in ND and AD subjects. The acute biomarker response to exercise and the effect on cognition has not been examined in aged or AD cohorts. We hypothesize that acute higher intensity exercise will elicit a greater blood lactate response (area under the curve, AUC) compared to acute moderate intensity exercise, and that this response will be greater in ND than in AD subjects. We further hypothesize that lactate AUC will track negatively with change in cerebral glucose metabolism and cognitive performance. Although we will focus on lactate, we will also quantify additional exercise-related biomarkers.

Our overall goal is to characterize the acute exercise response as it relates to brain glucose metabolism in aging and AD. We will also examine lactate metabolism, relationships with cognition, and the effect of exercise intensity. The KU ADC is a recognized leader in the study of exercise and metabolism in aged and AD populations, and puts us in a strong position to successfully achieve these aims.

## **B. Background and Significance**

Alzheimer's disease (AD) is the most common neurodegenerative disease, affecting over 5 million Americans, with this number expected to balloon to nearly 14 million by 2050. [1] Annual health care costs associated with AD exceed 200 billion dollars [2] which has led to the formation National Alzheimer's Project Act (NAPA). Goals of NAPA include the creation of a national plan to overcome AD, development of treatments to prevent, halt, or reverse AD, and improvements in early diagnosis and care of AD patients.[3]

Our team has been at the forefront research to characterize the impact of exercise on AD prevention and progression. We have shown that an exercise program improves cognitive (primarily executive) function in nondemented (ND) subjects in an exercise dose-dependent manner. [4] We have further shown that there is a positive relationship between cardiorespiratory fitness change and memory change in individuals with AD who participate in 6 months of aerobic exercise [5] and are currently investigating these effects in subjects with preclinical AD (ClinicalTrials.gov ID NCT02000583). However, not all individuals benefit from exercise, and the precise mechanisms by which exercise elicits a beneficial effect are unclear. We are currently exploring a variety of approaches ranging from molecular to neuroimaging studies to investigate these effects. One of the great knowledge gaps, however, is how little we know about the acute effects of exercise in AD. Most clinical trials, including our own, have been designed to assess metabolic outcomes at two fasting timepoints, before and after the intervention. However, the effects of each acute exercise bout on brain metabolism, and potential mechanisms by which cognition and memory may be affected, remain unclear. We will explore these factors in the current application. *Few groups are as well-positioned as ours to integrate cardiorespiratory fitness measures, acute exercise interventions, and advanced neuroimaging techniques.*

### **Exercise benefits the brain: rationale for understanding the acute exercise response in AD**

Longitudinal observational studies show a relationship between self-reported exercise and cognitive decline, [6-11] and higher physical activity in midlife and late life is associated with a reduced risk of developing late-onset AD.[12, 13] Furthermore, intervention studies have shown cognitive improvement following exercise in ND and MCI subjects. [4, 14-21] Cardiorespiratory fitness decline tracks with brain atrophy and progression of dementia severity in AD [22] and hippocampal volume has improved with a physical activity intervention in some studies of older adults. [20, 23] In our recent study of exercise in AD subjects, we did not see an overall improvement in memory in the intervention group, but change in cardiorespiratory fitness was positively correlated with change in memory.[24] The finding that cardiorespiratory fitness change is important in achieving memory effects in AD is consistent with work that shows a positive relationship between exercise-related cardiorespiratory fitness change and markers of cortical thickness and brain volume in ND, MCI, and AD subjects. [24-26] It is also consistent with work from our group and others that shows physical activity and fitness levels are associated with larger brain volume.[17, 27, 28]

Importantly, we postulate that cardiorespiratory fitness change is likely driven by the repeated, acute effects of each single, acute exercise bout that is additive over time. These acute effects include changes in peripheral biomarkers that readily cross the blood brain barrier but return to normal within a few hours. However, the effects of acute exercise on the brain are not well understood, especially in aged and AD populations, and at the intensities that are often used in exercise intervention programs. This presents a knowledge gap in the study of the beneficial effects of exercise in aging and dementia populations.

[figure not shown]
### Why study lactate?

The terms “lactate” and “lactic acid” are often used interchangeably and differ by only one proton. Lactic acid is still considered by some to be a waste product generated during exercise, and although controversy still remains regarding the role of lactic acid in muscle acidification,[29-31] there is substantial evidence that lactate plays a critical and beneficial role in a variety of tissues. [32-34] The production of lactate from pyruvate generates NAD+, a necessary intermediate for glycolysis. Peripheral lactate is transported to the liver for regeneration of pyruvate via the Cori cycle; however, lactate is transported throughout the entire body, and during physical exercise, lactate provides a key source of energy for muscle and brain [35-39]. Because lactate is used efficiently by the brain even at rest [40, 41], **we hypothesize that lactate is a critical energy source for the brain, and that generation of lactate during acute exercise directly impacts glucose metabolism in the brain.** We will explore the effects of acute exercise on brain glucose metabolism as well as the dynamics of acute exercise biomarkers, including lactate and related substances that may affect brain metabolism.

In 1994, it was shown that glucose use, lactate production, and lactate release increased with brain activation [42]. This spurred the “lactate shuttle hypothesis” which posits that astrocytes primarily metabolize glucose to lactate, which is shuttled to neurons for use in oxidative phosphorylation (Fig 1A). The concept of metabolic compartmentalization between brain cells is supported by expression of specific monocarboxylate transporter (MCT) isoforms, which transport lactate, in neurons compared to glia. Neurons express MCT2, which is characterized by a high affinity for lactate and limited expression profile, [43] while astrocytes primarily express MCT4, which has low lactate affinity and is implicated in efflux of lactate. [43, 44] It is suggested that astrocytes rely more heavily on glycolysis than neurons [45, 46]. Glycolytic enzyme fructose bisphosphatase is degraded in neurons, suggesting a limited ability of neurons to increase glycolysis and further suggests increased shunting of glucose metabolism towards the pentose phosphate pathway. [47] In short, glycolysis in neurons may be more critical for regeneration of antioxidants like glutathione, rather than generation of pyruvate for oxidation within mitochondria. Finally, studies of mice using FRET technology have shown that lactate can permeate both astrocytes and neurons, with evidence of an astrocyte-neuron lactate gradient. Lactate injection has been shown to increase neuronal lactate uptake relative to astrocytes. [48] Taken together, this molecular evidence suggests that interventions which increase peripheral lactate, such as aerobic exercise, may increase flux into neuronal cells.

### Lactate dynamics and exercise

In humans, there is a linear relationship between systemic lactate concentration and brain lactate uptake at physiological concentrations and lactate can contribute to as much as 60% of cerebral metabolism when transporters are saturated. [40] The kinetics of lactate entry into brain indicate the blood brain barrier is about half as permeable to lactate as glucose, but that intracellular uptake of lactate is greater. [49] Recent evidence suggests that the FDG signal is driven by glial glucose use, [50] and that increased supply of peripheral lactate may reduce the FDG-PET signal. [51, 52] Regardless of source, increased lactate supply should drop the FDG signal due to increased availability to both cell types.

**Fig 1. Schematic figure for the effect of exercise on brain glucose metabolism.** (A) It has been proposed that glycolysis within glia is a key source for neuronal energy at rest, likely via the intermediate metabolite lactate. B) Acute exercise increases circulating lactate levels, which can permeate the blood brain barrier and freely enter the brain. Lactate can be directly taken up into both neurons and glia, which would spare glucose and decrease the FDG signal.

**Human studies:** To date, most human studies of lactate and the brain have used lactate infusion and/or exercise, and were performed in healthy young men. A study using a lactate clamp and exercise showed that lactate oxidation during moderate exercise was improved by increasing lactate levels, sparing glucose and decreasing glucose production. [53] Two other studies demonstrated that acute exercise improved cognition, [54] and the cognitive improvement positively correlated with cerebral lactate uptake. [55] Finally, exercise at an intensity which increased circulating lactate levels decreased cerebral glucose metabolism (FDG-PET signal), while lower intensity exercise that did not increase peripheral lactate did not. [51] Although the decrease in cerebral glucose metabolism is proposed to be due to glucose sparing, as energy needs are met by lactate, [51] the cellular fates of glucose and lactate have not been measured directly in humans due to technological limitations. Nonetheless, the acute changes in cerebral glucose metabolism may represent an important measure of **cerebral responsiveness to exercise**. It may also predict changes in resting cerebral glucose metabolism that have been observed in longer exercise intervention studies. [56, 57] However, the effects of acute exercise on brain glucose metabolism have not been assessed in ND elderly or AD populations.

#### **Potential roles of related exercise biomarkers**

Although a lactate-specific relationship with cerebral glucose metabolism will be our focus for Aim 1, we will also examine five additional exercise-related biomarkers that affect the brain. These biomarkers will include brain-derived neurotrophic factor (BDNF), vascular endothelial growth factor (VEGF), transforming growth factor beta (TGF- $\beta$ ), irisin, and glucose. Our rationale for the selection of these specific exercise-related biomarkers follows. BDNF is a potential mediator of exercise-related brain benefit [20], but its acute response has not been analyzed in AD. Studies in human cell lines suggest that short-term lactate exposure increases BDNF expression in both cortical astrocytes and SY5Y cells. [58] Lactate is positively linked to both BDNF and VEGF levels following exercise, [59, 60] although it is unclear whether lactate drives these responses. In addition, in rodents, exercise-induced elevation of blood lactate increases TGF- $\beta$  in brain CSF [61, 62]. This may be of relevance as TGF- $\beta$  is implicated in the mobilization of fat-related energy substrates. We have indirect evidence that energy substrate use during fitness tests may differ based on AD diagnosis, which is discussed later (Fig 4). Furthermore, in rodents, inhibition of TGF- $\beta$  signaling decreased memory performance and long-term potentiation. [63, 64] Another modulator of fat metabolism and signaling is irisin. [65] Irisin is a relatively newly-recognized hormone that is induced during moderate intensity exercise [66] and has been linked to cognition in older adults at risk for dementia [67]. We and others have linked glucose to progression of AD and AD-related neuropathology, [68, 69] and in pilot studies we have observed that glucose and insulin are both acutely responsive to exercise, with large variation between individuals. Quantification of these important exercise- and cognition- related biomarkers will enhance our understanding of the acute exercise response in aged and AD populations.

#### **Acute vs. Chronic effects of exercise on brain glucose metabolism**

The directionality of change in brain glucose metabolism following acute exercise likely will not reflect the directionality of change in brain glucose metabolism following chronic exercise. While we expect to observe a decrease in glucose uptake following acute exercise due in part to the availability of lactate for oxidation, it has been shown that a 12wk exercise *intervention* is associated with an increase in brain glucose metabolism post-intervention. [56] Likewise, inactive individuals show reduced FDG signal with age, while active individuals do not, suggesting lifestyle attenuates the age-related drop in brain glucose metabolism. [70] Interestingly, pre-clinical studies have shown that acute exercise modulates a region-specific upregulation of monocarboxylate (lactate/pyruvate/ketone) and glucose transporters that remain elevated at least 18-24 hrs post-exercise [71]. Other work that examined immunostaining patterns of the glucose transporter isoform 1 (GLUT1) showed upregulation in motor cortex following exercise. [72] Although the effect on other transporter isoforms is unclear, this suggests that plasticity in GLUT1 expression may be related to neuronal activity. Over time, acute exercise-related effects may elicit changes in metabolic transporter expression and localization, and thus predict longer-term outcomes. For example, larger acute drops in brain glucose metabolism due to strenuous exercise may elicit greater/longer term change in expression of transporters and increased resting glucose metabolism, although this remains to be

tested. These ideas are outside of the scope of the current proposal, but the current work will lay the foundation for future investigations and trials to explore such mechanisms.

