### A. Study Type and Design:

This is a cross-sectional, observational study to determine the effect of acute exercise on cerebral glucose metabolism in cognitively healthy elderly (n=30) and Probable AD (n=30). There will be 4 study visits. Individuals will be recruited from the KU Alzheimer's Disease Center (KU ADC) Clinical Cohort and Eligibility Database. The study visits are explained below, and a timeline for the FDG-PET scan visits is given in Figure 2.

Figure 2A. Resting Visit Timeline

[figure not shown]
[figure not shown]

Figure 2B. Exercise Visit Timeline

uptake, the subject will sit quietly. Background factors (lighting, noise, etc.) will be identical between V2 and V3, with the only difference being the acute exercise bout (Fig 2, A-B). We will adhere to strict timing regarding blood draws, tracer injection, and scan time. Following the scan, a short battery of executive function tests (see detailed methods) will be administered (Table 2). \*V2 and V3 will be counterbalanced.

**Visit 2/3 (~90 mins):** V3 will consist of an FDG-PET scan in early morning, after an overnight (8hr) fast, following exercise. The timing for blood draws and PET scan will match V2. *For both visits we will inject the radiotracer at the timepoint that corresponds to completion of the 5 min warm-up.* In pilot work, we showed that blood lactate levels are elevated at this time using this exact exercise protocol (Fig 3). Following the scan, a short battery of executive function tests (see detailed methods) will be administered. \*V2 and V3 will be counterbalanced.

**Visit 4. (~30 mins):** We will obtain a structural MRI, which will enhance the analysis of the PET images.

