**Resting Protocol (Visit 2 or 3 – counterbalanced between subjects)**

Participants will arrive for FDG PET after having fasted for a minimum of 8 hours and will have a catheter placed for IV administration of FDG. Draw 1 will be performed right before FDG bolus is administered. Subjects will begin resting and will receive a single IV bolus of FDG minutes into resting. Draw 2 will be taken after 5 minutes of rest. Draw 3 will be taken after 20 minutes of rest. The participant will be moved to the PET scanner at minute 25 and Draw 4 will be taken at 30 minutes. The scan will start immediately at minute 35. After the scan is complete a blood draw will be taken at minute 45 and a short cognitive performance test (NIH Toolbox Cognition Battery) will be performed. The final blood draw will be taken after the testing is complete, at approximately minute 75.

**Acute Exercise Protocol (Visit 2 or 3 – counterbalanced between subjects):** Participants will report to the scan room for the baseline blood draw. After mounting the bicycle, subjects will be asked to begin exercise (warm-up) 5 min before the injection of FDG. One minute prior to warm up, while the subject is resting and sitting on the bicycle, Draw 1 will be taken. At time T0 the subject will pedal at 60-70 revolutions per minute at an equivalent of 40W for 2 minutes. The study coordinator will oversee the workload and provide instruction to the participant as needed. Over the next 3 minutes, the study coordinator will increase the workload to either 45-55% or 65-75% of HRR (depending on randomization group). Blood pressure will be

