monitored during the warm up. Four minutes after the warmup begins (1 min prior to FDG injection), Draw 2 will be taken. Immediately following the 5 min warm up, FDG will be injected through the IV catheter that was placed prior to exercise. Following injection, participants will maintain cycling at either 45-55% or 65-75% of their HRR for 15 min. We will use an electronically-braked cycle ergometer (Lode, Groningen, Netherlands) to precisely control HR and workload. Rating of perceived exertion (RPE) will be collected every 2 minutes to assess effort. Participants will maintain a consistent pedaling rate (60-70 rpm) as this may affect physiological variables. [111] Immediately following the 15 min exercise at the target intensity, Draw 3 will be taken. At this time, the participant will begin a cool down period that lasts 5 min. Blood pressure will be monitored during the cooldown. The participant will dismount the bicycle and move to the scanner table. Draw 4 will be taken at 30 minutes before the scan. After the scan is complete a blood draw will be taken at minute 45 and a short cognitive performance test (NIH Toolbox Cognition Battery) will be performed. The final blood draw will be taken after the scan is complete, at minute 75. We will provide up to 120mL of water as needed to account for any dehydration that may affect blood volume during exercise. The amount of water consumed by each participant during exercise will be noted by the study coordinator.

Cognitive performance analyses (Visits 2 and 3): Most work assessing acute cognitive change following exercise has focused on executive function testing. We will administer a short battery of cognitive tests using the NIH Toolbox Cognition Battery on an iPad 5 minutes following the end of the FDG-PET scan at minute 50. These will assess executive function, attention, processing speed and episodic memory, given data linking these domains with exercise and physical activity.[1, 112] Different versions of these tests will be used between the resting and exercise visits where available.

MRI Scan (Visit 4): Structural MRI will use a Siemens 3.0 Tesla Skyra MRI scanner. We will obtain high resolution T1 weighted (MPRAGE) images following the ADNI2 standard. High-res T1 weighted anatomic images provide gross anatomy with high gray-white matter contrast (MP-RAGE; 1x1x1mm voxels; TR=2300, TE=2.98, TI=900, FOV, 1mm thickness, flip angle 9°). Neuroimages will be processed via Freesurfer. [81]

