### **V. Data Analysis and Reporting**

#### **A. Statistical and Data Analysis:**

The primary statistical analyses for Aims 1-2 utilize paired, pre-, post- acute exercise measurements. As such, we will analyze the data using the two-sample, paired t-tests. This will contrast overall changes in

brain metabolism following acute exercise (i.e., pre- vs. post-exercise differences) and between the intensity groups (moderate vs. higher intensity). We will conduct residual analyses to assess the appropriateness of this methodology to evaluate assumptions of common variance, normally distributed errors, etc. In the event any of the measures do not conform to these foundational assumptions, the nonparametric analogs will be used instead, such as the Wilcoxon rank sum test of the within-subject pre- vs. post-exercise measures. These measures will follow the intent-to-treat principals. Though a randomized design, we will also construct exploratory analyses that incorporate other adjustments using ordinary least squares (OLS) regression on the change scores as the outcomes, also with residual analysis and modified approach if indicated. This will allow for model adjustment to further examine these relationships. One further relationship will involve combining the results of the AD and ND subjects in a single model as described in our Aims. We will use OLS in this context to test for interactions between AD and ND subjects with respect to the acute exercise response (moderate vs. higher intensity) for these pre-/post-exercise change score outcomes. Finally, we will model change score outcomes as functions of the various other change score measures. This approach will enable us to observe how changes in cerebral glucose metabolism are driven by acute-exercise influenced changes in circulating biomarkers. We will conduct similar residual analyses appropriate to the regression models utilized to ensure appropriate inferences are drawn. While descriptive and exploratory in nature, we anticipate that this approach will illuminate and/or confirm our pre-conceived metabolic processes that are related to the acute exercise response, and that it will help identify likely reasons for prior exercise trial successes and failures through mechanistic discovery. We believe this study fits perfectly within the study paradigm for PAR-18-877 by the NIA, which states that identifying precise cellular mechanisms will provide important therapeutic targets.

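### Visit order is counterbalanced but left out of the primary change-score tests, which costs precision; carry-over into the resting scan is a separate question that the plan leaves open

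*Combined protocol and SAP*

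**What the plan says.** Section II.A (Study Type and Design) gives each participant a resting and an exercise scan at Visits 2 and 3 and states that "V2 and V3 will be counterbalanced"; the protocol headings in II.E repeat this. About half would therefore have the exercise scan first. The split itself, and whether order is balanced within each diagnosis-by-intensity cell, are not stated. The two visits are meant to match, "with the only difference being the acute exercise bout". On timing, II.A says that "V3 will consist of an FDG-PET scan in early morning, after an overnight (8hr) fast, following exercise", with the other visit timed to match. That implies separate days, but the readable text gives no interval.

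Section V.A (Statistical and Data Analysis) says of the paired measurements: "As such, we will analyze the data using the two-sample, paired t-tests". No period, sequence or order term is named there. None is named in the exploratory OLS on change scores, whose adjustments are unspecified, or in the regional SUVR comparison under FDG-PET imaging in II.E, which allows t-tests or mixed models. For the cognitive battery, II.E adds: "Different versions of these tests will be used between the resting and exercise visits where available".

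Two statements in I.B bear on persistence. The subsection on acute versus chronic effects cites pre-clinical, region-specific transporter changes that "remain elevated at least 18-24 hrs post-exercise". The subsection on the rationale for studying the acute response says that peripheral biomarkers "return to normal within a few hours".

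**The concern.** Counterbalancing is a design device that the analysis should use. If the second visit differs systematically from the first (familiarity with the scanner, practice on cognitive tests, drift in measurement), the two orders have different expected change scores. A t-test that pools them counts this known difference as noise. The standard error is then too large, and power is lost in a trial with 15 participants per cell.

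A second, separate issue is whether the exercise bout still affects a resting scan that follows it. If so, counterbalancing does not cancel the effect, and the change score is biased in the exercise-first half.

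**Working it through.** **1. The plan's own figure.** Inputs from the sample size justification in V.A: 15 vs 15 AD participants; effect sizes 1.00, 1.25 and 1.50. Two-sided alpha of 0.05 is an assumption, since V.A does not state it. For a two-sample t-test on change scores with 28 df, the noncentrality is d × sqrt(15 × 15 / 30). Power is 75.3%, 91.0% and 97.7%, against the stated 75%, 91% and >95%. The figures reproduce, so the powered comparison is moderate versus higher intensity.

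**2. Model.** Let τ be the true exercise-minus-rest change, π the shift of the second visit relative to the first, and λ any carry-over that raises the resting scan after exercise. All are in SDs of the change score within one order.
- Rest first: expected change = τ + π
- Exercise first: expected change = τ − π − λ

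The documents give no value for π or λ. All values below are assumptions.

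**3. Period effect (λ = 0).** With equal numbers per order, π cancels from the mean and the pooled SD becomes about sqrt(1 + π²): 1.03 at π = 0.25 and 1.12 at π = 0.5. Fifteen cannot split evenly. An 8/7 split leaves π/15 in an arm mean, and 8/7 against 7/8 leaves 2π/15 between arms (0.067 SD at π = 0.5). If order is not balanced within cells, more remains: 10/5 against 5/10 leaves 2π × 5/15 = 0.33 SD at π = 0.5.

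Simulated two-sample t-test, 15 vs 15, effect size 1.25, π = 0.5, no order term:

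| Order split in the two arms | Power | Type I error |
|---|---|---|
| 8/7 and 7/8, imbalance favouring the effect | about 90% | about 3% |
| 8/7 in both arms | 86% | about 3% |
| 8/7 and 7/8, imbalance reversed | 82% | about 3% |

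With an order term (27 df), power is about 91% and type I error about 5% in all three rows. With order balanced and no period effect, the term costs almost nothing: 91.0% at effect size 1.25, and 75.2% instead of 75.3% at 1.00.

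**4. Carry-over (π = 0).** With half the participants exercise-first, the mean rest-to-exercise change shifts by λ/2. In the intensity contrast a common λ cancels: at 0.25 and 0.5 SD, type I error stays between 4% and 5%. Only a difference in λ between intensities biases that contrast, by about half the difference. For carry-over present only after higher intensity (40,000 simulated trials, orders 8/7 and 7/8):

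| λ, higher intensity only | Shift, no order term | Type I error, no order term | Type I error, with order term |
|---|---|---|---|
| 0.25 | 0.12 | 6.0% | 6.2% |
| 0.5 | 0.23 | 8.8% | 9.8% |
| 1.0 | 0.46 | 19.7% | 23.7% |

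The order term does not remove this bias.

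**5. Rest-first subset.** Its expected change is τ + π, so it is free of λ but fully confounded with π. If π is 0.25 or 0.5 and τ is zero, a paired test on 30 rest-first participants rejects 26% or 75% of the time. The intensity contrast within one diagnosis group has 7 or 8 per arm: power at effect size 1.25 is 61% (7 vs 8) to 64% (8 vs 8).

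**The case against.** The strongest reply is that counterbalancing already does its job. With order balanced, a period effect does not bias the mean, and ignoring it makes the test conservative. That stands, so this is a point about precision, not validity. At 0.25 SD the loss is small: 90% power with the same split in both arms. The clearest example, practice on cognitive tests, is not the primary outcome, and different test versions are planned where they exist. The exploratory OLS also already provides a place for an order term, although V.A does not name one.

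A reader might infer something stronger: that carry-over inflates the hypothesised drop and that the trial would produce false positives. Assuming 0.25 or 0.5 SD of carry-over in half the participants, the rest-versus-exercise test would reject under the null about 10% or 25% of the time at n = 30, and about 16% or 46% at n = 60. The arithmetic is right, but the documents do not support the inference:
- The sizes are assumed, and these rates do not apply to the powered 15 vs 15 contrast.
- The cited evidence is pre-clinical, region-specific and about transporter expression, not FDG signal. The same subsection treats a later rise in resting metabolism as untested.
- It covers lactate as well as glucose transporters, and I.B itself argues that more lactate supply lowers the FDG signal.
- SUVR is referenced to the cerebellum, so a uniform proportional rise would cancel, and the sign of any regional remainder is unknown.

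The statement about biomarkers normalising within hours does not settle the matter the other way, because it concerns the periphery, not brain transporters.

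Nor can one say that no interval was set. In the available copy of II.A, the start of the visit descriptions and the Figure 2 timelines are not readable. The detailed procedures in II.E give no interval.

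**Conclusion.** The point holds as one about efficiency. Leaving out visit order keeps a known source of variation in the error term. At an assumed 0.5 SD period effect, type I error falls to about 3% and power from 91% to about 82-90%; with no period effect, nothing is lost. This rests on order being balanced within cells, which the plan does not state.

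Carry-over is plausible but not shown. If present, half of it would enter the rest-to-exercise change, and half of any difference between intensities would enter the intensity contrast. Neither its size nor its direction can be taken from the documents. It has to be addressed through the visit interval and its justification, not through the order term.

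**What to change.** 1. In V.A, make the change-score OLS the analysis for both the intensity contrast and the overall rest-to-exercise change. Include visit order as a fixed term coded +1/2 and −1/2, for FDG, lactate and cognition. Centring makes the overall change the equally weighted average of the two orders, not the change in one of them.
2. State that order is balanced within each diagnosis-by-intensity cell, as nearly as 15 allows (8/7).
3. Confirm or state the interval between Visits 2 and 3, chosen by the sponsor, and reconcile it with the persistence window cited in I.B.
4. If a rest-first subset analysis is reported, label it a low-power sensitivity analysis that is free of carry-over but confounded with period.

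The cost is one degree of freedom, one model term, and a sentence each on allocation and scheduling. Power stays at about 91%, and no extra participants or scans are needed.
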